This Walk with Me study is a two-arm parallel-group randomised trial involving 348 older adults aged 60 years or over living in socio-economically disadvantaged communities. Individuals will be randomised to either a 12-week peer-led walking intervention group or a minimal intervention control group. Baseline measures will be collected before randomisation, at 12 weeks (post-intervention), six months (accelerometer only) and 12 months. An internal pilot will be included with pre-specified stop-go criteria. The independent Trial Steering Committee (TSC) will assess the feasibility of progressing past the first 6-month internal pilot period based on the recruitment rates of peer mentors and participants. Using a 'traffic light' system previously recommended,¹⁹ progression will be based on the percentage of the target sample achieved half way through the recruitment period (6-months): (a) proceed: $\geq 50\%$ of the total sample of peer mentors and participants recruited; (b) modify: 25-49% of the total sample of peer mentors and participants recruited; or stop: $< 25\%$ of the total sample of peer mentors and participants recruited. After six months, any required changes in the recruitment strategy and/or introduction of new recruitment pathways will be agreed with the TSC and the funder. The participants recruited in the pilot study will be included in the overall analysis. Qualitative data will also be collected at 12 weeks and six months. Process and economic evaluations will be nested within the trial.

Setting and Participants

The study will target community-dwelling older adults, aged 60 years or over living in areas of socio-economic disadvantage, defined as most disadvantaged quartile of electoral wards in NI, based on the NI Multiple Deprivation Measure (NIMDM) (www.nisra.gov.uk), which covers a large geographical area.

Recruitment

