After this, the participant will be encouraged to utilise these local opportunities for physical activity to maintain their activity. To support this transition, participants will be given specific advice on maintenance at the end of the intervention, which includes information about the health benefits of keeping their activity up and they will be encouraged to make individual plans to avail of specific physical activity opportunities in the form of group exercise or a personal physical activity plan.³⁴ Between months three and six, participants will be encouraged to continue to use the pedometer to monitor their activity levels and return their pedometer logs (Appendix 9) to their peer mentor.²⁸ This will be reinforced through a monthly telephone or online video call from their peer mentor between months three and six to encourage maintenance and review their ongoing engagement in activity.³⁵⁻³⁶ Health reasons are often cited in older adults physical activity research as a main contributor to attrition.³⁷ Therefore, any participant experiencing short-term health issues that affect their participation in physical activity will be encouraged to pick up again when they are able to. Where appropriate, participants will also be encouraged to utilise technology to support their physical activity, such as the Active 10 mobile phone app that helps individuals monitor their activity, and they can be signposted to other digital supports, for example, physical activity programme websites such as the 'Move with Mary' initiative detailed above. During the final six months participants will continue with the programme unsupported in what will be termed an 'independent' phase.³⁸

Peer Mentors

Peer mentor recruitment

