Peer mentors will be offered telephone or online video access to a health improvement officer for advice or support as well as online resources and access to a closed Facebook group to access support from other peer mentors. Additional follow-on support will be delivered to mentors during the programme. A health improvement officer will meet (online if necessary) with the peer mentors three times (once a month) to ensure that they are still comfortable with the content of the intervention, briefly refresh the original training, including the techniques of goal-setting and monitoring, address any technical problems which may arise e.g. when using online video calls, and any issues which may have arisen with participants (such as not turning up), and discuss the focus for the next phase of the intervention. They will be offered a certificate following training and will be reimbursed for all expenses such as mileage. They will be paired with participants of the same sex and from a similar community. Each mentor will have “responsibility” for up to five intervention participants. As in the pilot study, peer mentors will be provided with a Peer Mentor Participant Information Sheet (v1: 6th November 2021; Appendix 11) and individuals who agree to participate will be asked to provide written consent (v1: 6th November 2021; Appendix 12) before they complete the same outcome measures that the participants complete at the outset of the programme and again at 12 weeks, six months and 12 months. This will give them an insight into what participants have experienced as well as offer the opportunity to evaluate the potential impact of the programme on the physical activity and health of the peer mentors themselves.

Matching peer mentors to participants

As in the pilot study,¹⁸ mentors and intervention group participants will be matched by sex, geographic location and other information such as their activity likes, dislikes and habits.

During their initial meeting, the structure for a typical meeting will be outlined and participants and mentors will be encouraged to continue this format in order to support the development of a rapport between them and to facilitate delivery of the intervention content.

Control group

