Individuals allocated to the control group will be contacted by a health improvement officer based at the Institute for Public Health. They will be thanked for their participation and informed that they will be contacted at 12 weeks, 6 months and 12 months for follow-up assessments. They will be given a copy of the Public Health Agency's information booklets on active ageing (Appendix 13) and healthy eating (Appendix 14). They will not receive any additional physical activity support over the course of the research study. To encourage retention, they will be contacted again by a health improvement officer at nine months to confirm contact details. Participants in the intervention group will be contacted at the same time to encourage retention. After the final data collection point, they will be given the opportunity to discuss with a member of the research team the availability of local physical activity opportunities (e.g. local walking groups). In line with approaches used in our pilot study¹⁸ and other interventions in older adults,¹³ they will also be offered a pedometer and physical activity diary during this meeting.

Outcome Measures

Demographic and outcome measures will be measured across four time points, as presented in Table 2.

Table 2: Outcome assessment according to the Walk with Me logic model and pilot study.

Data Collection	Baseline	3M	6M	12M
Socio-demographic: age, sex, marital status, car ownership (Appendix 15)	✓			
Actigraph accelerometer	✓	✓	✓	✓
Anthropometry – weight, body mass index (BMI), waist circumference	✓	✓		✓
Resting blood pressure	✓	✓		✓
Short physical performance battery (SPPB) ⁴⁰	✓	✓		✓
Warwick-Edinburgh Mental Well-Being Scale (WEMWBS) ⁴¹⁻⁴² (Appendix 16)	✓	✓		✓
EQ-5D-5L questionnaire ⁴³ (Appendix 17)	✓	✓		✓

UCLA Loneliness Scale ⁴⁴ (Appendix 18) and the Lubben Social Network Scale ⁴⁵ (Appendix 19)	✓	✓		✓
Physical activity self-regulation scale ⁴⁶ (Appendix 20)	✓	✓		✓
Physical activity and social activity self-efficacy ⁴⁷ (Appendix 21)	✓	✓		✓
Physical activity and social activity outcome expectancy ⁴⁸ (Appendix 22)	✓	✓		✓
Service use questionnaire (Appendices 23-25)	✓	✓		✓
Unintended consequences or adverse events		✓		✓

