following participant feedback accordingly. Standard unit costs will be used to cost resources. Responses to the EQ-5D-5L at baseline, 12 weeks and 12 months will be converted to utilities using the tariff recommended by NICE at the time of analysis.⁵⁸ We will use the area under the curve method to calculate QALYs.⁵⁹ To deal with missing data, we will explore the quantity of missing data and report on the missing rates for the different cost components and outcomes, by study group. We will also explore the nature of the missing data.

Since the relatively short time horizon of the trial will not capture the potential long-term health impact of the intervention, trial data will be incorporated into a long-term economic model with a lifetime horizon. We will conduct a literature review prior to designing the model to ensure we have the most up to date data on lifetime disease incidence, utilities and costs related to physical activity. The model is most likely to be a Markov state-transition model as these are particularly useful for modelling lifetime costs and health outcomes and have been used previously to assess the long-term cost-effectiveness of other physical activity interventions.⁶⁰⁻

⁶³

For both within trial and long term analyses we will perform deterministic sensitivity analysis to explore key assumptions and probabilistic sensitivity analysis (PSA)⁶⁴ to account for uncertainty arising from imprecision in the economic data. The PSA will generate bootstrapped replications of the incremental cost effectiveness ratio which will be plotted on the cost-effectiveness plane and used to construct a cost-effectiveness acceptability curve: this will depict the probability of the Walk with Me intervention being cost-effective compared to usual care at different willingness-to-pay per QALY thresholds. We will consider the performing subgroup analyses and this will be in keeping with the main statistical analyses. A detailed health economic analysis plan will be written in advance.

Methods for data collection

Outcome measures will be assessed at baseline, post-intervention (12 weeks from the start of the intervention in the intervention group or equivalent timing for the control group), 6 months (accelerometer only) and 12 months after baseline, in person, by a Research Assistant, who will be blind to group allocation.

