The aim of these focus groups will be to: (1) understand the experience of participants and mentors; (2) explore if SCT and the logic model describe the experience of participants; (3) explore the barriers and facilitators to longer term maintenance of activity; (4) explore the intervention BCTs used as part of making the initial changes in physical activity and to maintain activity at six months. Anonymity and confidentiality for reporting will be ensured. Topic guides (Appendix 31) will facilitate discussions. Audio recordings of focus groups will be transcribed and uploaded into QSR NVivo (v12) along with field notes. Analysis will explore the logic model, guided by the five stages of the Framework approach:⁷¹ familiarisation; identifying a thematic framework; indexing; charting; mapping and interpretation.

Assessment of unanticipated outcomes

This is a low risk intervention, and we do not anticipate any serious adverse events. Adverse event reporting will follow the Health Research Authority guidelines on safety reporting in non-clinical trial investigational medicinal product studies (CTIMPs). Participants will be encouraged to report adverse events (e.g. musculoskeletal problems or falls) to the study team. Adverse events reported by participants will be recorded on a standard proforma (Appendix 32).⁷²

Serious adverse events, defined as an unexpected occurrence resulting in death, threat to life or hospitalisation or otherwise considered medically significant by the investigators will be recorded and assessed by clinical members of the study team who are not directly involved in the day-to-day running of the trial for causality and expectedness, using the definitions provided in Table 3.

Table 3: Serious Adverse Event (SAE) causality definitions	
Causality assessment	Description
Unrelated	There is no evidence of or rationale for any causal relationship.
Likely to be related	There is evidence, and a rationale, to suggest a causal relationship and other possible contributing factors can be ruled out.

If, in the opinion of the clinical co-investigator, an SAE occurring to a research participant is classified as related to the intervention, then the Chief Investigator will be responsible for reporting it to the Sponsor and to the research ethics committee which issued the favourable ethical opinion, using the SAE report for non-CTIMPs (published on the Health Research Authority website) within 15 days of becoming aware of the event.

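### Adverse events are asked about only at 3 and 12 months, which leaves up to 9 months of recall and puts the between-arm comparison at risk of unequal ascertainment

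*Protocol*

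**What the plan says.** All references are to the protocol.

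- **Status of the outcome.** The opening summary lists adverse events among the secondary outcomes. The second project aim is to assess between-group differences in secondary outcomes.
- **Scheduled enquiry.** In Table 2 (Outcome Measures) the row "Unintended consequences or adverse events" is ticked at 3M and 12M and blank at 6M.
- **Unscheduled route.** Assessment of unanticipated outcomes states: "Participants will be encouraged to report adverse events (e.g. musculoskeletal problems or falls) to the study team". It adds: "Adverse events reported by participants will be recorded on a standard proforma (Appendix 32"). That appendix is not shown.
- **The 6-month assessment.** Study Design describes follow-up at 12 weeks and then "six months (accelerometer only) and 12 months". Methods for data collection gives the mode: "6 months (accelerometer only) and 12 months after baseline, in person, by a Research Assistant, who will be blind to group allocation".
- **The 9-month contact.** Under Control group, a health improvement officer contacts controls at nine months to confirm their details. The intervention arm is contacted at the same time to support retention. No adverse-event question is mentioned for either arm.
- **Mentor contact, intervention arm only.** Walk with Me Intervention describes weekly meetings for 12 weeks, then a "monthly telephone or online video call from their peer mentor between months three and six".
- **Mentor support.** Under Ongoing support for peer mentors, the monthly meetings between officer and mentors cover, among other things, "any issues which may have arisen with participants". The example that follows in the text is non-attendance, not harm.

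**The concern.** Two features of the schedule matter.

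The first is recall. After the 3M enquiry nobody is asked again until 12M. The protocol's own examples, musculoskeletal problems and falls, include minor events that are easily forgotten or misdated over many months. The gap covers months 3 to 6, when intervention participants are still being encouraged by their mentors to walk.

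The second is opportunity to report. Intervention participants regularly talk to someone connected with the study about their recent activity and any difficulties. Controls have no counterpart. An event mentioned to a mentor may prompt a report to the team that a control would never make. If such reports are counted with answers to the scheduled questions, part of any between-arm difference could reflect reporting rather than harm. Conversely, a real difference arising in the maintenance phase could be lost to forgetting.

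At stake is the interpretation of a named secondary outcome. An analysis plan can separate reports by source if source is recorded, but it cannot recover events that were forgotten before anyone asked.

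**Working it through.** The protocol gives no adverse-event rate, reporting probability or precision target, so there is no planned figure to reproduce. The check is of the schedule.

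**1. Recall windows.** From Table 2, enquiries fall at months 3 and 12.
- First window: 3 − 0 = 3 months.
- Second window: 12 − 3 = 9 months.
- An event in months 3 to 6 is between 12 − 6 = 6 and 12 − 3 = 9 months old when first asked about.

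**2. Mentor contacts by window** (from Walk with Me Intervention).

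| Window | Intervention | Control | Next scheduled enquiry |
|---|---|---|---|
| Months 0–3 | 12 weekly meetings | 0 | 3M |
| Months 3–6 | about 3 monthly calls | 0 | 12M |
| Months 6–12 | 0 | 0 | 12M |

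The total is 12 + 3 = about 15, but 12 of these fall in the short window that the 3M enquiry closes in both arms. In the 9-month window the difference is about 3 calls, all before month 6. The 9-month contact is common to both arms.

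**3. Is there a stated path from mentor to adverse-event record?** Mentor training covers feedback to the project team. The officer discusses participant issues with mentors and reports progress to the team. Contact diaries, meeting recordings and focus groups also involve intervention participants and mentors only. Each could bring an event to light in one arm. None is described as an adverse-event route, and the stated route, participant to study team, is worded alike for both arms.

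**4. Can the size be estimated?** Suppose the true risk is equal in both arms and a proportion c of those with an event is captured. The observed risk ratio is then c(intervention) / c(control). Assume 0.90 in the intervention arm:
- control 0.90: 0.90 / 0.90 = 1.00
- control 0.80: 0.90 / 0.80 = 1.125
- control 0.50: 0.90 / 0.50 = 1.80

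These capture values are assumptions. Nothing in the protocol selects among them, and the range includes no bias at all. Identical enquiries at 3M and 12M also recover some unvolunteered events in both arms, which pulls the ratio towards 1. The exercise shows the mechanism, not a magnitude.

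**5. Effect of using existing contacts.**
- Enquiries at 3, 6 and 12 months: windows of 3, 3 and 6; longest 6 months.
- Enquiries at 3, 6, 9 and 12 months: four windows of 3; longest 3 months.

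**The case against.** A reader might infer that the comparison is already unequally ascertained. The protocol does not support that. The scheduled enquiry is the same in both arms and belongs to assessments made by a blinded Research Assistant. The spontaneous route is worded alike for both arms, and mentors are given no adverse-event role. The passage on participant issues has non-attendance as its example.

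A reader might also treat the difference in total contacts as a measure of the bias. It is not one: most mentor contacts fall before the 3M enquiry, where recall is at most 3 months in either arm.

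Other points on this side are fair:
- The protocol nowhere says that volunteered and solicited reports will be pooled. Tabulation by source can be left to the analysis plan, and the proforma may record source and onset date.
- Long recall applies only to events not reported as they occur. The service-use questionnaire and participant diary described under Cost-utility analyses give a partial record, in both arms, of events that led to care.
- The protocol regards the intervention as low risk, and serious events have their own procedure.

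All of this stands, and it limits the point to a risk. It does not remove the 9-month gap, which Table 2 fixes and no later analysis can close. Nor does it explain why two contacts common to both arms go unused for this purpose.

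**Conclusion.** The point holds as a modest design weakness, not as an error or a contradiction. It is established that enquiry is scheduled only at 3 and 12 months, that unvolunteered events in the second window depend on up to 9 months of recall, and that mentor contact exists in one arm only. Differential reporting is a plausible consequence if volunteered and solicited events are counted together. The protocol neither shows that this will occur nor allows its size to be estimated. The likely direction, more complete reporting in the intervention arm, rests on the assumption that talking with a mentor prompts reports. Because the correction uses contacts already planned, it is worth making even though the size of the problem is unknown.

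**What to change.** 1. Add the adverse-event questions to the 6-month assessment, in the same words for both arms. Tick 6M in that row of Table 2, and amend the accelerometer-only description in Study Design and Methods for data collection.
2. If feasible, ask the same questions from a script at the existing 9-month contact in both arms.
3. State that the between-arm comparison rests on events elicited at scheduled enquiries. List events learned through mentors, or volunteered between contacts, separately and without comparison. Serious events continue to be reported whatever their source.

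**Cost.** A few minutes per contact, the edits above and one sentence on analysis.

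**Downsides.** Answers at 6 months may hint at allocation to the blinded Research Assistant. The 3M enquiry already carries that risk. Asking last protects measures taken earlier in the same visit but not those at later visits, and the accelerometer is in any case worn over the following 7 days. The officer's role at nine months also includes supporting mentors, so that enquiry cannot be assumed blinded, which is why it should be scripted.

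### The SAE definition requires unexpectedness and then has expectedness assessed with no definition of it, and Table 3 has no class for a plausibly related event with a competing cause

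*Protocol*

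**What the plan says.** All the relevant rules are in the protocol section on assessment of unanticipated outcomes.

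- **Definition.** "Serious adverse events, defined as an unexpected occurrence resulting in death, threat to life or hospitalisation". The sentence continues with a further route: "or otherwise considered medically significant by the investigators will be recorded and assessed by clinical members of the study team".
- **Assessment.** The events so defined are assessed "for causality and expectedness, using the definitions provided in Table 3".
- **Table 3, *Unrelated*.** "There is no evidence of or rationale for any causal relationship".
- **Table 3, *Likely to be related*.** "There is evidence, and a rationale, to suggest a causal relationship and other possible contributing factors can be ruled out".
- **Reporting trigger.** The report to the sponsor and the ethics committee, within 15 days of awareness, is required where, in the clinical co-investigator's opinion, "an SAE occurring to a research participant is classified as related to the intervention".
- **Ordinary adverse events.** "Participants will be encouraged to report adverse events (e.g. musculoskeletal problems or falls) to the study team". Those reports go on a standard proforma.

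The section also states that no serious adverse events are anticipated, and it refers in general terms to Health Research Authority safety-reporting guidelines.

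**The concern.** Two rules fail when followed as written.

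First, seriousness and expectedness are normally separate properties of an event. Here unexpectedness is part of what makes an event an SAE, yet expectedness is also to be judged after the event has qualified. The table named for that judgement says nothing about expectedness. Two assessors could disagree on whether the same admission is an SAE at all, and the text would not settle it.

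Second, a causality scale that controls reporting should give every event a class. This one names two extremes. In adults aged 60 or over, with no upper age limit under the eligibility criteria, a fall on a walk in someone with another possible cause is a realistic case, and it has no class.

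At stake are whether reports reach the sponsor and the ethics committee, and what a published count of related SAEs would mean. The primary outcome, randomisation, power and main analysis are not affected.

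**Working it through.** No arithmetic in the plan bears on this point, so the check is one of logic.

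**Step 1: the definition against the assessment.** Let S be a serious outcome (death, threat to life, hospitalisation) and U be unexpected. The definition admits an event if S and U both hold, or if the investigators consider it medically significant. Expectedness is then assessed among events already admitted.

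- Through the first route, every admitted event is already unexpected, so the later assessment can only return the entry condition.
- An event with S but not U does not enter by the first route. It depends on the investigators' discretion, and on one grammatical reading *unexpected* governs that route too.
- Table 3 is cited for both judgements. Its two rows describe causality only, so the expectedness judgement has no stated standard.

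**Step 2: coverage of Table 3.** The rows use three yes/no criteria: evidence (E), rationale (R), and other contributing factors ruled out (O). That gives 2 × 2 × 2 = 8 combinations.

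| E | R | O | Class |
|---|---|---|---|
| yes | yes | yes | Likely to be related |
| yes | yes | no | none |
| yes | no | yes | none |
| yes | no | no | none |
| no | yes | yes | none |
| no | yes | no | none |
| no | no | yes | Unrelated |
| no | no | no | Unrelated |

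*Likely to be related* covers 1, *Unrelated* covers 2, and 8 − 1 − 2 = 5 have no class.

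**Step 3: a looser reading.** Suppose *Unrelated* is read as lacking evidence or lacking rationale. It then covers the 6 combinations in which E and R are not both present. *Likely to be related* still covers 1, and 8 − 6 − 1 = 1 remains without a class. That one is evidence and rationale present with another factor not excluded, which is the case that matters most. The gap survives either reading.

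**Step 4: consequence for reporting.** The 15-day report requires a related classification. An event in the unclassified group has no stated route to that classification and no stated route to *Unrelated*. The protocol leaves its handling undetermined.

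**The case against.** The strongest reply is that little is lost in practice, and several parts of it stand.

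- **Catch-all.** The definition also admits events the investigators consider medically significant, so a hospitalised fall could still be taken in. This stands, but it is discretionary and does nothing for Table 3.
- **No SAEs anticipated.** If none is anticipated, and the text shows no list of expected ones, almost any serious event is unexpected. This narrows the first problem considerably. Naming falls as an example of adverse events is not the same as expecting hospitalised falls. The causality gap is untouched.
- **Events are still recorded.** A reader might infer that such events would go wholly unrecorded. The documents do not support that: participant-reported events go on the proforma with no expectedness filter, Table 2 schedules adverse events at 3 and 12 months, and the service-use questionnaire is completed at 12 weeks and 12 months. What can be lost is recording and assessment *as an SAE*. A death is the weak spot, since it cannot be self-reported.
- **External guideline.** It may well be sound, but its text is not in the protocol, and a general reference does not settle which explicit definition an assessor should apply.

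A reader might also infer that weekly mentor meetings bias the comparison of adverse events between arms. The protocol does not make those meetings a route for collecting adverse events; participants report to the study team. Table 2 and the data-collection section already provide for assessment at 3 and 12 months by a research assistant blind to allocation.

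**Conclusion.** The point holds as a defect in stated rules. The SAE definition and the later expectedness assessment are circular, expectedness is referred to a table that does not define it, and the causality classes are not exhaustive although reporting depends on them. The causality gap is the firmer part, because no other sentence in the section closes it. The circular definition matters less if the investigators treat every serious event as unexpected.

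Its size can be given only in logical terms: 5 of 8 combinations have no class on the plain reading, and 1 of 8 on the looser one. The documents give no hospitalisation rate and no share of events with a competing cause, so the number of affected events cannot be estimated. A reader might infer that the related class would be almost empty. That does not follow: an event with some evidence fails *Unrelated* as clearly as it fails *Likely to be related*, and the trigger is a clinician's opinion. The text shows ambiguity without showing its direction.

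The conclusion assumes that assessors follow the protocol's wording and that neither the proforma nor the cited guideline, neither of which is reproduced, supplies the missing definitions.

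**What to change.** 1. Remove *unexpected* from the SAE definition, so that an event is serious by its outcome or by the medically significant criterion alone.
2. Assess expectedness as a separate step with its own definition, and stop citing Table 3 for it.
3. Make Table 3 exhaustive. One way is to add a *possibly related* class for events with some evidence or rationale where other factors cannot be excluded, and to state that it counts as related for reporting.
4. Align the wording of the 15-day trigger and the proforma with the revised classes. The trigger says *related*, which is not at present the label of either class.

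The cost is rewording one paragraph, one table and one form. No visit, sample size or intervention component changes. The downside is a few more expedited reports.
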